connect the computer to the Internet, the average time spent on the website, pages viewed, information searched for, and access times. Participants can disable cookies to restrict this monitoring.

After enrollment, we will collect data from participants remotely at 34-36 weeks of pregnancy, and at 1, 2, 5, and 8 weeks postpartum and 6 months postpartum. We collect birth hospitalization and feeding data via the birth electronic medical record after birth. At 34-36 weeks of pregnancy, we will collect questionnaire data regarding breastfeeding self-efficacy, breastfeeding intentions, and maternal employment (covariate impacting breastfeeding) via an electronic REDCap survey link sent to participants via email. At 1, 2, 5, and 8 weeks postpartum, we will collect data including breastfeeding self-efficacy, anxiety, depression, breastfeeding knowledge, perceived milk supply, infant feeding status, feeding activities, breastfeeding support, and receipt of Text4Baby texts via REDCap survey (emailed link to participants). All participants will be assigned a number (chronological based on enrollment order), and this will be used on all data collection instruments (including emailed surveys), rather than participant's real name. Research staff or the PI will review survey responses within two days of completion to assess missing/non-sensical data. Research staff will attempt to contact participants by phone to resolve missing or non-sensical data upon identification of the issue. Time for participants to complete remote surveys is estimated at no more than 30 minutes. They may begin a survey and return to it. Participants will have approximately 1 week to complete surveys. A reminder email will be sent at 3 days if no survey is received. We will attempt to call participants up to three times to complete questionnaires over the phone if no electronic survey is completed after the email reminder at 3 days. Note that we will also call participants by phone without emailing a survey first if they prefer a phone call. The timepoints chosen for data collection were based on the higher prevalence of perception of insufficient milk and early breastfeeding cessation in the first 1-2 months postpartum.

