## STATISTICAL ANALYSIS PLAN

Data will first be screened for anomalies (e.g., outliers, non-normality, missing data, imbalances between groups). If anomalies are encountered, appropriate remedial strategies will be applied

(e.g., data transformation, imputation, statistical adjustment of covariates, etc.) prior to primary analyses. We will analyze efficacy outcomes using an intention-to-treat approach, but also conduct sensitivity analyses and perform comparisons based on protocol deviations (e.g., comparisons between participants who do and do not receive all texts, participants in the intervention group who receive Text4Baby). Between group (each time point) and group  $\times$  time differences will be examined graphically and via generalized mixed-effects modeling for all outcome variables of interest. For our main outcome of breastfeeding exclusivity at 8 weeks and other categorical outcome variables (e.g., any breastfeeding at each follow-up), we will use chi-square test statistics and logistic regression (if statistical adjustment is needed) to determine between-group differences. For continuous-type outcome variables (e.g., perceived milk supply/confidence scores), we will assess between-group differences at postpartum follow-ups via analysis of variance procedures (e.g., ANCOVA, ANOVA) or analogous nonparametric methods.

We will descriptively analyze study participation, attrition, and intervention use (e.g., proportions with 95% CIs). We will also explore possible predictors of participation (yes, no) and intervention use (yes, no) with group comparative statistics (e.g., independent sample t-tests and chi-square test statistics or binary logistic regression for continuous and categorical variables, respectively). The PI will code interview data for major themes using Atlas TI. The interview script will be modified on a continual basis to include new perspectives broached by participants.

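### Does the plan need a rule for perceived milk supply scores once a woman has stopped breastfeeding?

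*Combined protocol and SAP*

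**What the plan says.** The protocol's Study Protocol section schedules remote surveys at weeks 1, 2, 5 and 8 after birth. Their content includes "perceived milk supply, infant feeding status, feeding activities". These visits were chosen because of the "higher prevalence of perception of insufficient milk and early breastfeeding cessation in the first 1-2 months postpartum". Nothing restricts the milk supply items to women still breastfeeding, and staff telephone participants to resolve missing answers. The score is not among the measures listed for enrollment or for 34-36 weeks.

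The Statistical Analysis Plan states "We will analyze efficacy outcomes using an intention-to-treat approach". For scores it says "For continuous-type outcome variables (e.g., perceived milk supply/confidence scores), we will assess between-group differences at postpartum follow-ups via analysis of variance procedures", and it examines group and group-by-time differences "via generalized mixed-effects modeling for all outcome variables of interest". On data quality: "Data will first be screened for anomalies (e.g., outliers, non-normality, missing data, imbalances between groups"; then "If anomalies are encountered, appropriate remedial strategies will be applied", with examples ("e.g., data transformation, imputation, statistical adjustment of covariates, etc.) prior to primary analyses"). The sensitivity analyses it illustrates concern receipt of texts, not stopping. Any breastfeeding at each follow-up is compared between arms, and attrition is described.

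**The concern.** A score for perceived milk supply has an uncertain meaning once a woman no longer breastfeeds. The visits fall where stopping is expected, and the trial's theory ties low confidence both to stopping and to perceived insufficient milk. If stopped women drop out of the score analysis and MILK keeps more women with low scores breastfeeding, the MILK group's average among those remaining is pulled down. The comparison would then lean against MILK on the very problem its texts target, while carrying an intention-to-treat label.

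The late choice of remedy adds to the worry. A blank may mean that the woman stopped, which is itself an outcome. Different ways of filling it move the estimate in different directions, and the screening step looks at group imbalances and is not said to be blinded.

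**Working it through.** The documents give no continuation rate, correlation, score SD or sample size, so there is no figure of the plan's own to reproduce. All inputs below are assumed, and scores are in SD units.

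**1. Visit-wise ANOVA if stopped women give no score, no true effect.** Let p be the proportion continuing, r the correlation between the score and the tendency to continue, and λ(p) = φ(z_p)/p. The difference, MILK minus control, is r × [λ(p_MILK) − λ(p_control)].

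λ(0.60) = 0.644, λ(0.65) = 0.570, λ(0.70) = 0.497, λ(0.75) = 0.424.

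| Control v MILK continuing | r = 0.3 | r = 0.5 | r = 0.7 |
|---|---|---|---|
| 60% v 65% | -0.02 | -0.04 | -0.05 |
| 60% v 70% | -0.04 | -0.07 | -0.10 |
| 60% v 75% | -0.07 | -0.11 | -0.15 |

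For example, 0.5 × (0.497 − 0.644) = -0.07. With 100 per arm, 60 and 70 women remain, and with SD 1 the standard error is √(1/60 + 1/70) = 0.18. The bias is then about 0.4 of a standard error.

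**2. When the bias vanishes.** It is zero if r = 0 in both arms, or if both continuation and r are the same in both arms. Equal continuation alone is not enough: at 60% in each arm, with r = 0.3 under MILK and 0.5 under control, it is 0.644 × (0.3 − 0.5) = -0.13 SD.

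**3. Mixed model.** Four visits were simulated with 10 runs of 40,000 women, total SD 1, intraclass correlation 0.6, lower scores raising the chance of stopping, MILK lowering it, and no true effect. The model was a random-intercept model with known variances.

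| What drives stopping | Continuing at week 8 | ANOVA | Mixed model |
|---|---|---|---|
| Previous observed score; all have a week-1 score | 60% v 79% | -0.13 | 0.00 |
| Current, unseen score; all have a week-1 score | 60% v 79% | -0.15 | -0.07 |
| Previous score, but 17% v 8% stop before week 1 with no score | 53% v 74% | -0.15 | -0.05 |

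The ANOVA is therefore conditional on continuing. The mixed model is conditional on having at least one postpartum score and relies on missing at random. How far it is off depends on the stopping process.

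**4. Picking a rule afterwards.** At 60% v 75% and r = 0.5, giving stopped women a fixed score f makes each arm's mean r·φ(z_p) + (1 − p)·f. With f = -1 the difference is -0.091 − (-0.207) = +0.12; with f = -2 it is -0.341 − (-0.607) = +0.27. The sign can change, but only through a scoring rule that the SAP does not mention.

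False positives were simulated with no arm difference, 60% continuing in each arm, 50 to 200 per arm and within-woman correlation 0.5. The two analyses that the SAP names, taken together, give at least one p < 0.05 in 5-7% of trials. Adding last score carried forward and a rank composite raises this to 10-13%, but neither is in the plan.

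**The case for a change.** The strongest case for a change is that the gap is real whatever the survey does. No rule is written, the plan itself expects early stopping, and intention-to-treat is claimed without saying what it means for a score that may lose its meaning. Telephone follow-up recovers unreturned surveys but does not define milk supply for a woman who has stopped. The mixed model is not a full answer either: with no measurement before birth, a woman who stops before the week-1 survey and is then not scored contributes nothing. A few sentences of SAP text would be cheap.

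Most of this stands as description. What does not follow is that carrying out the plan as written gives a wrong answer. Read plainly, the protocol asks every participant for the score. The instrument, its skip pattern and its scoring are not in the documents, so exclusion of stopped women is possible but not shown.

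Nor would the added sentences settle the matter. They would have to leave open who is asked and which estimand applies, and each choice costs something. A comparison among continuers gives up the randomized contrast, hypothetical and principal-stratum estimands need untestable assumptions, and a composite mixes continuation with perceived supply. Counts of women scored, stopped and not reached can already be produced from feeding status and the planned attrition summary.

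**Conclusion.** No change to the plan is needed. The silence on post-cessation scores is missing detail on one continuous outcome, and an analyst can fill it by reading feeding status beside the score and describing any continuer-only comparison as such.

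If stopped women were in fact unscored, the visit-wise comparison would be biased by roughly -0.02 to -0.15 SD over the assumed range (60% v 65-75% continuing, r = 0.3 to 0.7, the same r in both arms, no true effect). The mixed model would range from essentially unbiased to about -0.07 SD in the scenarios simulated, which have wider continuation gaps. The direction rests on two further assumptions: that MILK raises continuation and that low scores lead to stopping. Neither the exclusion nor any of these inputs is given in the documents. Exclusivity at 8 weeks and any breastfeeding remain defined for women who have stopped, so the trial's main conclusion does not depend on this point.

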## STUDY PROTOCOL

Study staff will approach pregnant individuals for enrollment who are attending a prenatal appointment between 13-25 weeks gestation. Potential participants who would like time to think over their enrollment decision will be offered a consent form or handout to take home and review, and can contact the study coordinator later if interested. Confirmed eligible participants providing written informed consent will be randomized via computer-generated simple randomization to the experimental or control intervention group (MILK intervention or Text4Baby, respectively). For patients not recruited at the primary enrollment site at MWH (e.g., website; study flyer), arrangements will be made to meet to explain the study, obtain informed consent, randomize to a group, and collect baseline data.

At enrollment, study staff will collect baseline data including demographic, obstetric and breastfeeding history, anxiety, breastfeeding self-efficacy, breastfeeding attitude, breastfeeding intentionality, breastfeeding knowledge, and breastfeeding support via oral administration of paper-based or electronic questionnaire on a study iPad. Data will be inputted into and managed in REDCap (secure, password protected and backed up data management system through University of Pittsburgh). We will also collect contact information for follow-up data collection (email, telephone numbers) and, for participants in the experimental intervention (MILK) group, we will provide written and oral instructions regarding text message frequency and how to stop or reduce volume of text messages (or withdrawal from study). We will provide participants in the control intervention (Text4Baby) instructions about how to sign up for the freely available Text4Baby services. The baseline visit is expected to last an hour or less and will occur either in the prenatal exam room or private MWH space.

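### Four continuous scores are collected at enrollment and again postpartum, but the SAP does not commit to adjusting for the enrollment score

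*Combined protocol and SAP*

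**What the plan says.** The Study Protocol section has these constructs scored at enrollment: "anxiety, breastfeeding self-efficacy, breastfeeding attitude, breastfeeding intentionality, breastfeeding knowledge, and breastfeeding support". For the surveys at 1, 2, 5 and 8 weeks after birth it lists "breastfeeding self-efficacy, anxiety, depression, breastfeeding knowledge, perceived milk supply, infant feeding status, feeding activities, breastfeeding support". Four constructs are on both lists: self-efficacy, anxiety, knowledge and support. Self-efficacy is also measured once in late pregnancy: "At 34-36 weeks of pregnancy, we will collect questionnaire data regarding breastfeeding self-efficacy, breastfeeding intentions, and maternal employment".

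The Statistical Analysis Plan section has three statements that bear on how these scores are compared:

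- For continuous outcomes, "we will assess between-group differences at postpartum follow-ups via analysis of variance procedures (e.g., ANCOVA, ANOVA) or analogous nonparametric methods".
- If screening shows problems, such as non-normality or group imbalance, remedies follow: "e.g., data transformation, imputation, statistical adjustment of covariates, etc.) prior to primary analyses".
- In parallel, between-group and group-by-time "differences will be examined graphically and via generalized mixed-effects modeling for all outcome variables of interest".

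None of the three names a covariate for the continuous scores. None says which method applies when, or which of the two analyses of the same scores takes precedence.

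**The concern.** A score on the same construct, taken at enrollment, is usually among the best predictors of the later score. A comparison that uses it gives a narrower interval at no cost in data. Plain ANOVA and the ordinary two-sample rank test do not use it. The SAP permits both, and where it does mention adjustment it makes it depend on what screening shows. That misses the main reason to adjust: the gain in precision comes from the correlation between the two scores and is available whether or not the arms happen to differ at enrollment.

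What is at stake is the precision of the secondary comparisons that test how the intervention works. The protocol's conceptual model puts self-efficacy at the centre of breastfeeding behavior, so a needlessly wide interval on that score weakens the evidence on mechanism. An adjusted analysis chosen after looking at the data is also less convincing than the same analysis fixed beforehand.

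**Working it through.** **Inputs.** The documents give no sample size, alpha, power, SD, effect size or enrollment-to-postpartum correlation, so there is no stated figure to reproduce. Everything numerical below rests on an assumed correlation r between the enrollment score and the postpartum score. Where power is shown, two-sided alpha 0.05, 1:1 allocation and a standardized difference of 0.5 are also assumed.

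**Step 1: which scores qualify.**

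| Construct | Enrollment | 1, 2, 5, 8 weeks |
|---|---|---|
| Self-efficacy | yes | yes |
| Anxiety | yes | yes |
| Knowledge | yes | yes |
| Support | yes | yes |
| Perceived milk supply | not listed | yes |
| Depression | not listed | yes |

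The argument covers the first four rows only.

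**Step 2: precision.** With n per arm and SD σ, the unadjusted difference has variance 2σ²/n. Adjusting for the enrollment score leaves about 2σ²(1 − r²)/n. The ratio is 1 − r², the interval narrows by 1 − √(1 − r²), and the equivalent sample-size factor is 1/(1 − r²).

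| r | 1 − r² | Variance saved | Interval narrower by | Equivalent sample factor | Power, if 80% unadjusted |
|---|---|---|---|---|---|
| 0.3 | 0.91 | 9% | 5% | 1.10 | 84% |
| 0.5 | 0.75 | 25% | 13% | 1.33 | 90% |
| 0.7 | 0.51 | 49% | 29% | 1.96 | 98% |

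Under the assumptions above, 63 women per arm give 80% power unadjusted. With adjustment 58, 48 or 33 per arm would do at r = 0.3, 0.5 or 0.7.

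**Step 3: does the formula hold in small samples?** In 4,000 simulated trials per setting, the ratio of adjusted to unadjusted variance was 0.93, 0.77 and 0.52 at 25 per arm for r = 0.3, 0.5 and 0.7. At 100 per arm it was 0.91, 0.75 and 0.53 (formula: 0.91, 0.75, 0.51). The gain does not need a large trial.

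**Step 4: does the planned mixed model already secure the gain?** That depends on a choice the SAP does not state.

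- Enrollment score as covariate, or as a time point with a common mean in both arms: the gain is recovered.
- Enrollment score as a time point with free arm means and complete data: the contrast at a visit equals the raw mean difference, so nothing is gained.
- Change from enrollment: relative to the unadjusted comparison (= 1) the variance is 2(1 − r), which is 1.4, 1.0 or 0.6 at r = 0.3, 0.5 or 0.7. This is worse than unadjusted below r = 0.5, and worse than covariate adjustment (0.91, 0.75, 0.51) at all three values.

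**The case against.** **The plan already covers this.** ANCOVA is named first in the list, and a mixed model is planned for every outcome. That is fair, and a reader who infers that the SAP commits to an unadjusted test goes beyond the text. But ANCOVA is one example among alternatives with no covariate attached, and Step 4 shows that the mixed model may or may not use the enrollment score to advantage. The gap is an open choice, and a short clarification closes it.

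**The size is unknown.** This stands. Enrollment is at 13-25 weeks of gestation and the outcomes follow birth, so the correlation may be modest. The instruments are not named, and prenatal and postpartum versions may differ. At r = 0.3 the interval narrows by only 5%. Nothing in the documents supports the upper end of the range over the lower.

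**An open choice of test inflates false positives.** A reader might infer a type I error near 8%. Simulation does give 7.8% to 8.2% with 100 per arm and r = 0.5, both assumed, but only if all three tests are run and the most favourable is reported. The SAP describes screening followed by remedies, not selection on p-values. One simulated rule of that kind (rank test if normality is rejected, otherwise ANCOVA if the enrollment scores differ significantly, otherwise ANOVA) gave 4.4% with normal and 4.8% with skewed data over 10,000 null trials. The 8% is a worst case that the wording does not exclude. It is not a property of the plan.

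**The SAP's own example does not fit.** Its example of a continuous outcome is perceived milk supply or confidence. Perceived milk supply has no listed enrollment score, so the precision figures do not apply to it. Confidence may mean self-efficacy, to which they do.

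**Conclusion.** The point holds as a gap in specification. For self-efficacy, anxiety, knowledge and support, the SAP allows an analysis that ignores enrollment scores the trial has already collected, and it ties adjustment to what screening finds. The consequence is lost precision, not bias: 9%, 25% or 49% of the variance at assumed correlations of 0.3, 0.5 or 0.7, with the true value unknown.

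It is limited to secondary continuous scores. A reader might carry it over to the main outcome, but that is exclusive breastfeeding at 8 weeks, a binary measure to which these figures do not apply. The result assumes a roughly linear relation between the two scores. It does not require the prenatal and postpartum versions to share a metric, because a covariate need only be correlated with the outcome. The textual gap is certain; its practical size is not. It is worth correcting because the correction is free.

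**What to change.** In the Statistical Analysis Plan section, for these four scores, replace the open list of methods with one prespecified analysis:

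- Make the mixed model already planned (or ANCOVA, if a single visit is of interest) the sole main analysis of each score, reporting the arm difference at 1, 2, 5 and 8 weeks.
- Include the enrollment score of the same construct as a covariate, whatever imbalance is observed.
- Do not use the 34-36 week self-efficacy score as a covariate. Texts start at 25 weeks, so that score can already reflect the intervention.
- Label unadjusted, transformed and rank analyses as sensitivity analyses. Alternatively, name a rank analysis that adjusts for the enrollment score as the fallback, with the condition for its use stated in advance.

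For perceived milk supply and depression, state one method in advance as well, with no claim of a same-construct baseline. Covariance structure and any further covariates are for the trial statistician to choose.

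The cost is a few sentences in the SAP, written before outcome data are examined by arm. No new data, visits or participants are needed.
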